- No other demographic, clinical, or identifiable patient information (e.g., name, MRN, DOB) will be stored. The signed consent form will be retained separately in the sites regulatory binder as required by UAMS institutional policy, but will not be linked to study data.

Data Capture and Storage

Both the standard endoscopic tower and the modified portable system will record media for each specified location.

Source capture:

The modified Sony camera transmits recordings wirelessly to a secure, encrypted UAMS-device.

Standard tower images are stored on the institutional network per routine workflow.

Transfer and storage:

Study media will be exported, de-identified, and stored on a secure UAMS OneDrive folder accessible only to authorized study investigators. During the de-identification process, all direct and indirect identifiers will be removed, including patient name, date of birth, medical record number, encounter number, date of service, and any facial or other uniquely identifying features if present. Each file will be assigned a coded study ID and the link between this coded ID and the participants identity will not be maintained. A temporary linking log containing the study code and direct identifiers will be created for the purposes of confirming eligibility, tracking consent, and ensuring accurate file matching. This linking log will be stored separately

Title: Portable Endoscopic Camera System Using Modified Action Camera for Endoscopic Sinunatal Examination
PI: [name]
Institution: University of Arkansas for Medical Sciences

from all study data in a secure, encrypted, access-restricted UAMS One-Drive folder. Access will be limited to only PI and IRB approved study staff. Once all recordings have been verified and permanently de-identified, the link between the coded ID and the participants identity will be destroyed using UAMS-approved deletion methods preventing recovery. Only fully de-identified files will be retained and used for analysis.

De-identification and Coding

Before analysis, all recordings will be permanently de-identified to remove any HIPAA identifiers or metadata. Each image/video set will be assigned a numeric study code solely for matching the modified and standard system images from the same patient and same nasal side. No re-identification will be possible once coding is complete.

Data Evaluation

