Three attending physicians experienced in nasal endoscopy will independently grade the anonymized images using a 5-point Likert scale (1 = useless to 5 = excellent). Grading will occur exclusively on coded media files, with no patient identifiers visible at any stage.

Statistical Analysis

All data analysis will be performed by researchers at the Jones Eye Institute (JEI), University of Arkansas for Medical Sciences. Analysts will have access only to de-identified images and coded data, with no links to patient identifiers.

Descriptive statistics (mean, median, and standard deviation) will be used to summarize image-quality scores from both the standard and modified endoscopic systems. Nonparametric tests, including the Wilcoxon signed-rank test, will be applied to compare paired image-quality scores between the two systems to determine whether the modified endoscopic exam performs better, equivalent, or worse than the standard exam. Inter-rater reliability among the three physician graders will be assessed using the Intraclass Correlation Coefficient (ICC).

A total of 40 participants will be enrolled. This sample size provides sufficient power for within-subject comparisons, allowing detection of meaningful differences in image quality while accounting for potential variability across raters and minor data loss.

Sample size justification

A total of 40 participants will be enrolled. This sample size is appropriate for a paired comparison study in which each participant provides image-quality scores for both the modified system and the standard endoscopic system.

Title: Portable Endoscopic Camera System Using Modified Action Camera for Endoscopic Sinunasal Examination
PI: [name]
Institution: University of Arkansas for Medical Sciences

The primary analysis will use the Wilcoxon signed-rank test, which is commonly used for paired ordinal data. A formal power analysis for the Wilcoxon test will be completed by a statistician during the final analysis phase. However, based on typical assumptions used for paired nonparametric tests, a sample of 40 paired observations is generally sufficient to detect a small/moderate difference in Image quality with acceptable statistical power (80%) at the standard $\alpha=0.05$ level.

The sample size also provides a buffer for minor variability in image quality ratings across raters. Overall, enrolling 40 participants is expected to provide sufficient data to compare the two imaging systems.

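### No rule covers a view that a system fails to deliver; by default it drops out of the paired comparison, which favours whichever system fails more often

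*Combined protocol and SAP*

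**What the plan says.** Under Data Capture and Storage the protocol assumes full capture: "Both the standard endoscopic tower and the modified portable system will record media for each specified location". The portable camera sends its recordings wirelessly, while tower images go to the institutional network in the usual way.

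Under Data Evaluation, three attendings grade coded media files, and nothing else, on a scale of "1 = useless to 5 = excellent". The scale has no grade for a view that was not obtained, and nothing assigns grade 1 to such a view.

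Under Sample size justification, "The primary analysis will use the Wilcoxon signed-rank test, which is commonly used for paired ordinal data". Under Statistical Analysis, the paired test is to show "whether the modified endoscopic exam performs better, equivalent, or worse than the standard exam". The same section mentions loss once, when it says that the sample size is adequate while "accounting for potential variability across raters and minor data loss". No loss rate, definition, missing-data method, capture-rate outcome or sensitivity analysis is given.

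**The concern.** In a device comparison, giving no image is a result, and arguably the worst one. Clinical utility is one of the rated attributes, and a system that shows nothing at a site has no utility there. If such views leave the analysis without trace, the paired difference describes only the sites where both systems worked.

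The portable system has possible failure routes that the tower does not share: an improvised endoscope coupling and wireless transfer. If it fails more often, the plan as written would not show it, and a finding that the two systems perform alike could rest on omitted failures. Without a rule, how to handle failures would be decided after the scores are known.

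**Working it through.** **1. The plan's own figure.** The plan claims 80% power at alpha 0.05 with 40 pairs for a small to moderate difference. It gives no effect size, so the figure can only be back-solved. I assume a two-sided test and a Wilcoxon efficiency of 0.955 relative to the paired t-test:

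- Detectable standardized difference = (1.960 + 0.842) / √(40 × 0.955) = 2.802 / 6.181 = 0.453.
- With 10% of pairs lost (36 left): 0.453 × √(36 × 0.955) − 1.960 = 0.696, which is power of 76%. At 5% and 20% loss, power is 78% and 71%.

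As a matter of power alone, modest loss is indeed minor. The question is bias, which sample size cannot absorb.

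**2. Hidden mean difference.** Let both systems average q when a view is captured. Let the portable system fail at rate f and the tower at rate g, with failures unrelated to quality. With incomplete pairs dropped, the expected difference (portable minus tower) is 0. With failures scored 1 it is

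[(1 − f)q + f] − [(1 − g)q + g] = (f − g)(1 − q).

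The documents give none of f, g or q, so all are assumed:

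| f | g | q | Hidden difference |
|---|---|---|---|
| 5% | 0 | 4 | 0.05 × (−3) = −0.15 |
| 10% | 0 | 4 | 0.10 × (−3) = −0.30 |
| 15% | 0 | 4 | 0.15 × (−3) = −0.45 |
| 10% | 0 | 4.5 | 0.10 × (−3.5) = −0.35 |
| 10% | 2% | 4 | 0.08 × (−3) = −0.24 |
| 10% | 10% | 4 | 0 |

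**3. Chance of detecting it.** I simulated 40 participants with five sites each, scores rounded to 1–5, the same latent mean of 4.2 for both systems, and SDs of 0.4 between participants and 0.7 between sites (all assumed). The test was a two-sided signed-rank test on the participant mean, with 10% portable-only failures:

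| Failure pattern | Failures scored 1 | Failures dropped |
|---|---|---|
| Independent by site | about 88% | about 5% |
| Whole portable pass lost | about 20% | about 5% |

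Two other ways of summarizing, with failures scored 1, fall near the lower end: 21% with the median of five sites and 24% with one score per participant. The plan does not say how sites are combined, so no single figure can be chosen. In the independent-site case essentially all 40 participants still contribute a pair after failed sites are dropped, so the reported N would not reveal the loss.

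**4. If the poorest views are the ones lost.** With one score per participant (latent mean 4, SDs 0.5 and 0.6, assumed) and 10% portable failure confined to its lowest-scoring views, dropping pairs gives a mean difference of +0.09. The portable system is then wrongly found better in 11% of trials.

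**The case against.** A reader might infer that the plan classes failed portable views as minor data loss and excludes them. It does not say so. That phrase belongs to a sample-size sentence, is undefined, and is tied to neither system. Omission follows from the grading and pairing rules together with silence, not from a stated policy.

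A reader might also infer that blurred or out-of-focus views escape. They do not: the file exists and can be graded 1. Only views with no gradable file are affected, which is a narrower problem.

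Transfer loss is partly guarded against. Recordings are verified and matched through the linking log before the link is destroyed, and nothing says that a failed transmission loses the recording. That is a check on files, not a scoring rule.

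The direction of bias is conditional. The documents give no failure rate for either system, and both work with rigid endoscopy of the same nose, so anatomical access may limit them alike. With equal failure unrelated to quality there is no bias.

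Finally, scoring every failure as 1 could create a bias of its own. The portable examination always comes second, in an added 3–5 minutes without further topical anesthetic spray, so only it is exposed to a pass cut short for tolerance or time. Charging that to the camera would confuse order with image quality. It is also debatable whether a composite of quality and reliability should be the sole primary analysis. Both points stand and narrow the remedy. They do not supply the missing rule.

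**Conclusion.** The point holds as a gap in the plan: no rule covers an undelivered view, and the default hides any excess of failures in one system. Under portable-only failure and a tower score of 4, the hidden difference is -0.15 to -0.45 points for assumed failure rates of 5% to 15%. At 10%, detection would range from about 20% to about 88% with failures scored 1, against about 5% with failures dropped. These sizes rest on assumed rates, means, SDs and site aggregation; only the direction, given unequal failure, is robust. The documents do not support the stronger claim that the portable result will be inflated, because they do not show that it fails more often. The change should be made before grading starts, since it is cheap and cannot credibly be settled once the scores are known.

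**What to change.** - Add to the data elements, for each required site and each system, whether the view was captured or failed and why (device, transfer, pass stopped early, other). Complete it at the visit, before the linking log is destroyed.
- Report capture-failure rates and reasons by system.
- Keep the complete-pairs signed-rank test. Beside it, prespecify an analysis in which an attempted view with no gradable file for device or transfer reasons scores 1 for that system. Apply the rule to the tower and the portable system alike.
- Make no claim that the systems are equivalent unless both analyses agree.
- Report passes stopped early for tolerance or time separately and do not score them 1, because only the second examination is exposed to them.

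The cost is one extra field per site and system, one extra analysis, a short protocol amendment, and a possibly less favourable result for the portable system. If failures are rare, the two analyses will barely differ.

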There is no more than usual risk of endoscopic nasal examination and the second set of images will require only an additional 3-5 minutes and will not require any additional topical lidocaine spray. The camera and the virtual reality glasses are not in direct contact with the patient. In addition, the camera will be covered by a sterile bag for additional protection of the patient. Another risk to study participants is the potential for loss of confidentiality of study data. Images of the patients will be deidentified and given a study code to protect patients' confidentiality. Measures to protect the confidentiality of study data will be implemented as described in the Data Handling and Recordkeeping section below.

Benefits of the study

There will be no direct benefits to the study participants; however, knowledge gained from the study could potentially benefit patients in the future who may benefit from this examination portable examination method. This design would allow more portable use of this examination virtually everywhere in the hospital setting e.g.: in the emergency and inpatient departments as well as in outreach services. In addition, this design can be very helpful for clinical care in underserved communities as well as in developing countries.

Title: Portable Endoscopic Camera System Using Modified Action Camera for Endoscopic Sinunasal Examination
PI: [name]
Institution: University of Arkansas for Medical Sciences

Data Handling and Recordkeeping

Data Elements and Timing of Collection

Each participant will undergo two sequential nasal endoscopic examinations during a single clinical visit. The standard endoscopic imaging will occur first, followed immediately by imaging using the modified Sony Action Camera system, requiring approximately 3–5 additional minutes.

The following data elements will be obtained for research purposes:

- Endoscopic video clips and still images of nasal anatomical sites (inferior meatus, inferior concha, middle concha, middle meatus, nasal septum, and any visible pathology such as polyps, ulcers, or mucosal thickening).
- A coded study ID (number) used to pair the modified-system recordings with the standard-system recordings for the same nasal side of the same participant.
- Image quality ratings assigned by three attending physicians using a 5-point Likert scale assessing resolution, quality, and clinical utility.

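### The 80% power claim for a 'small/moderate' difference rests on unlisted assumptions: under standard ones, 40 pairs support it for a moderate difference but not for a small one, and the formal calculation comes too late to justify the sample size

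*Combined protocol and SAP*

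**What the plan says.** The section Sample size justification makes the Wilcoxon signed-rank test the primary analysis and states that "a sample of 40 paired observations is generally sufficient to detect a small/moderate difference in Image quality with acceptable statistical power (80"%). It sets alpha to 0.05. The only basis offered is that this is "based on typical assumptions used for paired nonparametric tests"; the assumptions are not listed. The same paragraph says: "A formal power analysis for the Wilcoxon test will be completed by a statistician during the final analysis phase".

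The section Statistical Analysis adds that the sample size gives sufficient power while "accounting for potential variability across raters and minor data loss", with no loss rate. It gives the purpose of the paired test as to "determine whether the modified endoscopic exam performs better, equivalent, or worse than the standard exam". No margin for equivalence is set.

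The scores behind the pairs are described under Data Elements and Timing of Collection as "Image quality ratings assigned by three attending physicians using a 5-point Likert scale assessing resolution, quality, and clinical utility". Under De-identification and Coding, the study code serves for "matching the modified and standard system images from the same patient and same nasal side". The plan does not say how graders, domains, anatomical sites and nasal sides reduce to one pair of scores per participant.

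**The concern.** A power statement needs a number of pairs, an alpha, a power, a test and an effect in a stated unit. The plan gives the first four and replaces the fifth with an adjective that spans a wide range. Forty pairs may be ample at one end of that range and well short at the other. The calculation that would settle this is scheduled for when every participant has been enrolled and the number is fixed.

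This matters because of how the result may be read. The study sets a low-cost portable system against the standard tower, and the test is expected to support one of three conclusions, including equivalence. A reader told that small differences are detectable may take a non-significant result to mean that even a small deficit has been ruled out. If power at the small end is low, that inference fails.

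**Working it through.** **Inputs from the plan:** 40 pairs; alpha 0.05; power 80%; Wilcoxon signed-rank test.

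**Inputs the plan does not give (assumed here):** a two-sided test, since the stated purpose covers both directions; one score per participant; 40 complete pairs; roughly normal paired differences. The labels small (0.2 SD) and moderate (0.5 SD) follow a common convention that is not in the protocol.

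**1. The plan's own figure.** The 80% cannot be reproduced, because no effect size is stated. The question can be turned round: which effect has 80% power with 40 pairs?

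**2. Detectable difference, in SDs of the paired differences.**
- Normal approximation: (1.960 + 0.842)/√40 = 0.443.
- Paired t-test (noncentral t): 0.454.
- Wilcoxon, normal differences (efficiency 3/π, √(3/π) = 0.977): 0.454/0.977 = **0.465**.
- 36 evaluable pairs (an assumed 10% loss): 0.480/0.977 = **0.491**.

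Variants with 40 pairs:
- One-sided, normal differences: 0.400/0.977 = 0.41.
- Two-sided, Laplace differences (simulated): about 0.40.
- One-sided, Laplace differences (simulated): about 0.345.
- Two-sided, minimum Wilcoxon efficiency 0.864: 0.454/√0.864 = 0.49.

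The range over these variants is about 0.35 to 0.49.

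**3. Power across the range (two-sided Wilcoxon, 40 pairs, normal differences).**

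| Difference (SD of paired differences) | Power, efficiency formula | Power, simulation | Non-significant |
|---|---|---|---|
| 0.20 | 0.225 | 0.224 to 0.228 | about 77% |
| 0.30 | 0.439 | 0.441 to 0.445 | about 56% |
| 0.35 | 0.558 | 0.561 to 0.568 | about 44% |
| 0.465 | 0.80 | 0.802 | about 20% |
| 0.50 | 0.853 | 0.853 to 0.854 | about 15% |

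Simulated 5-point ratings with ties and zero differences (one rating, or the mean of three) gave 23 to 24% at 0.20, 57 to 59% at 0.35 and 81 to 82% at 0.47. The ordinal scale does not change the picture.

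**4. If the unit is the SD of the raw scores.** The effect in SDs of the differences is d/√(2(1 − ρ)), where ρ is the within-pair correlation. The detectable d is therefore 0.465 × √(2(1 − ρ)):

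| ρ (assumed) | 0 | 0.3 | 0.5 | 0.7 | 0.8 | 0.9 |
|---|---|---|---|---|---|---|
| d with 80% power | 0.66 | 0.55 | 0.47 | 0.36 | 0.29 | 0.21 |

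The ρ needed for 80% power is 1 − (d/0.465)²/2:
- d = 0.2: 1 − 0.185/2 = 0.91.
- d = 0.3: 1 − 0.416/2 = 0.79.
- d = 0.5: 1 − 1.156/2 = 0.42.

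**5. Precision that 40 pairs give.** The expected half-width of a 95% CI for the paired difference is t(0.975, 39)/√(40 × 3/π) = 2.023/6.180 = 0.33 SD of the paired differences. A simulated Hodges-Lehmann interval gave 0.324.

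**The case against.** The strongest reply is that nothing in the plan is computed wrongly. The stated power is true near the conventional moderate value, and the wording may mean an intermediate effect rather than 0.2 SD. That stands: this is an unsupported statement, not an arithmetic error.

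The unit could also rescue the claim. In raw-score SDs, a difference of 0.21 is detectable if the within-pair correlation is 0.9. If three graders' scores are averaged, 0.465 SD of the averaged difference equals 0.465 × √((1 + 2r)/3) SD of a single grader's difference, or 0.32 to 0.40 if graders' differences correlate at an assumed r of 0.2 to 0.6. This stands too, and it is why 0.47 must not be presented as the only point from which the claim holds. But each rescue needs a unit and a correlation that the plan does not state.

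On equivalence, a reader might infer that the plan will declare the systems equivalent whenever the Wilcoxon test is non-significant. The documents do not say so. They also plan means, medians and SDs for both systems, so the conclusion need not come from the test alone. What remains is that the test is given the task of separating better, equivalent and worse, with no margin and no rule against that reading.

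Finally, the protocol calls the study a proof-of-concept exploration, and such a study may be sized pragmatically. That defends the number 40, but not an explicit 80% power claim that cannot be checked.

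**Conclusion.** Wrong as written. On the assumptions of a two-sided test at 0.05, one score per participant, 40 complete pairs and roughly normal paired differences, 80% power is reached at about 0.47 SD of the paired differences, or about 0.49 SD with 36 pairs. Varying sidedness and distribution moves this to between about 0.35 and 0.49 SD. In that unit the claim is supported for a moderate difference and not for a small one; in raw-score SDs it cannot be judged without the within-pair correlation. The deferred power analysis cannot justify the sample size.

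A reader might infer that 40 participants are too few. The documents do not support that: they set no target difference against which 40 could fall short. The share of non-significant results (44% at 0.35 SD, 77% at 0.2 SD) is the ordinary type II error under assumed effects. It shows why non-significance must not stand in for equivalence, not that the study will reach a false conclusion.

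**What to change.** Keep 40 participants.

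1. Before any scores are compared, name the single participant-level primary score (how graders, domains, sites and nasal sides are combined). Replace the 80% sentence with the detectable difference, its unit and its assumptions. For example: 40 complete pairs give 80% power (two-sided alpha 0.05, Wilcoxon signed-rank, one score per participant, roughly normal paired differences) for about 0.47 SD of the paired differences, or about 0.49 SD if 36 pairs are evaluable. Update the figures if the chosen score calls for it. Keep 'small' only if a stated unit and within-pair correlation support it.
2. Delete the power analysis planned for the final analysis phase.
3. Report the paired difference (for example Hodges-Lehmann) with its 95% CI, and state that a non-significant Wilcoxon test will not be reported as equivalence.

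The cost is wording, one decision on the score and one short calculation, with no extra patients or visits. The stated detectable difference becomes less favourable, and equivalence can no longer be concluded from non-significance.
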